12.2. Description of statistical methods

A fully detailed statistical analysis plan will be developed and signed by the chief investigator prior to any data analysis being conducted. In brief, the analysis will incorporate the following:

Safety and reactogenicity

All SAEs will be presented for each group using descriptive analyses. Counts and percentages of each local and systemic solicited adverse reaction from diary cards, and all unsolicited AEs, and AEs of special interest will be presented for each group. Comparisons between the arms will be made using Fisher's exact test.

Immunogenicity

Highly skewed ELISA data will be log-transformed prior to analysis. The geometric mean concentration (GMC) and associated 95% confidence interval (CI) will be summarised by computing the anti-log of the mean of the log-transformed data.

The GMRs and CIs post boost will be calculated for each of the heterologous arms when comparing to the homologous arm.

Spike-specific T cell responses (ELISPOT) will be presented as geometric means and confidence intervals, or medians and interquartile ranges if non-normally distributed after log-transformation.

Comparisons of continuous immunogenicity data between different arms or at different time points will be made using a t-test if normal distribution can be rendered after log-transformation. Otherwise, Mann Whitney U test will be used.

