Accordingly, this study will determine the side effect profile, and the immune responses of heterologous and/or fractional COVID-19 vaccination schedules in adolescents, using BNT162b2 as a first dose, and a second dose administered from 8 weeks later of either BNT162b2 (full or one third dose) or NVXCoV2373 (full dose). Following the JCVI recommendation on 29th November 2021 that all 12 to 15 year-olds should be offered a second dose of BNT162b2 vaccine, the study design was amended to focus on immune response to BNT162b2. After this date, participants will be randomised 1:1 to either full or one-third dose BNT162b2 for their second vaccination. Participants will no longer be randomised to the Novavax arm of the study to prioritise the arms of the study that are likely to be more policy relevant. This does not reflect any concern regarding the safety or immunogenicity of the Novavax vaccine. A further review of the study design will be undertaken following an interim analysis in late 2021, and with input from the study Trial Steering Committee.

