7.3. Study groups

A total of up to 270 (+ up to an additional 10%) participants will be enrolled and randomised (1:1:1) as below:

Group	Arm	Prime (Day 0)	Boost (day 56)
	1	BNT162b2	BNT162b2
	2	BNT162b2	BNT162b2 (one-third dose)
	3	BNT 162b2	NVXCov2373

After 29th November 2021, the enrolment of participants who have received their first dose of COVID-19 vaccine in the community will be temporarily suspended. Only participants who have received their first dose of COVID-19 vaccine in the study will be randomised to a second dose. They will be randomised (1:1) as below:

Group	Arm	Prime (Day 0)	Boost (day 56)
	1	BNT162b2	BNT162b2
	2	BNT162b2	BNT162b2 (one-third dose)

Randomisation will be performed at the time of the second dose, and stratified by study site and anti-nucleocapsid IgG status at baseline where available.

The study will be single-blind, i.e. while staff involved in study delivery will be aware of what vaccine schedule the participant is receiving, the participant themselves will remain blinded to their boost vaccine. This blind will be maintained by applying a masking tape over the vaccine syringe as detailed in the study clinical study plan. Laboratory staff will also be blinded to the vaccine schedule received.

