9.4. Randomisation

Computer generated randomisation list will be prepared by the study statistician. Participants will be randomised 1:1:1 to the three study groups. After 29th November 2021, participants will be randomised 1:1 to the two study groups.

Participants will be randomised using block randomisation. Random block sizes of 3 and 6 will be used before 29th November 2021, and random block sizes of 2 and 4 will be used after 29th November 2021. Randomisation will be performed at the time of the second dose, and stratified by study site and anti-nucleocapsid IgG status at baseline (where available).

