23. APPENDIX A: SCHEDULE OF PROCEDURES

Study timeline	Screening	D0	D56	D14 post boost	D28 post boost	D132 post boost	D236 post boost
Study window		Within 120 days of screening	Day 56–70 post prime vaccine at D0 or Day 56 + post prime vaccination in community	Day 12-17 Post D56	Day 28-42 post D56	Day 112-152 post D56	Day 224-252 post D56
Pre - screening online consent	X*						
Informed consent	X	X					
Medical history	X	X					
Interim medical history		X	X	X	X	X	X
Physical examination (as required)	(X)	(X)	(X)	(X)	(X)	(X)	(X)
Urine test (Pregnancy) (if required)		(X)**	X				
COVID-19 vaccination		(X)**	X				

COVID-19 immunogenicity bloods		(X)**	X	X	X	X	X
Troponin and NT-proBNP blood test		(X)**	X	X	X		
Saliva and nasal fluid test (if participant consents)		(X)**	X	X			
Diary review			X	X	X		
SAE/AESI check			X	X	X	X	X

* Pre - screening online consent. Restricted to taking a limited medical history online, contacting the GP for further medical record if required and telephone screening visit(s)

**Procedures performed only if prime dose administered in the study

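### Section 12.2 was not adapted when the Novavax arm closed, so as written its Novavax comparison takes in later controls who could not have been allocated Novavax

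*Protocol*

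**What the plan says.** Section 12.2 names one reference arm for all immunogenicity comparisons: "The GMRs and CIs post boost will be calculated for each of the heterologous arms when comparing to the homologous arm". The test is fixed in outline: "Comparisons of continuous immunogenicity data between different arms or at different time points will be made using a t-test", with Mann-Whitney as the fallback. For solicited and unsolicited reactions, "Comparisons between the arms will be made using Fisher's exact test". No term for period or priming route is named, and no limit is set on which homologous-arm participants enter.

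The design changed during recruitment. Section 2 says "Participants will no longer be randomised to the Novavax arm of the study", and section 9.4 says "After 29th November 2021, participants will be randomised 1:1 to the two study groups". From the same date section 7.3 states that "the enrolment of participants who have received their first dose of COVID-19 vaccine in the community will be temporarily suspended" and that "Only participants who have received their first dose of COVID-19 vaccine in the study will be randomised to a second dose". Before then, participants could enter either unvaccinated or after a community first dose (section 9.6).

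The timing of the second dose differs by route. Appendix A gives the window as "Day 56–70 post prime vaccine at D0 or Day 56 + post prime vaccination in community". Sections 7.3 and 9.4 stratify randomisation by site and, where available, baseline anti-nucleocapsid status, but not by priming route. Section 12.1 still works from 90 per arm.

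**The concern.** The full-dose BNT162b2 arm spans two recruitment periods; the Novavax arm exists only in the first. A full-dose participant randomised after 29 November 2021 had no chance of receiving Novavax and came from a population restricted to study-primed adolescents. If such participants serve as controls for Novavax, the comparison mixes the vaccine effect with whatever else changed between the periods: calendar time, the share primed in the community, the prime-boost interval and exposure to infection. The protocol admits previously infected participants (section 5) and lets newly infected ones continue (section 7.4), so infection history can shift over time.

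This touches both the GMR and the Fisher's exact comparisons of systemic reactions, which are the primary outcome measure. Novavax is the only boost with a different vaccine, and section 12.4 says the interim analyses are meant to inform policy on the second dose.

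**Working it through.** **1. The plan's own figure.** Section 12.1 gives minimum detectable GMRs for 90 per arm, 90% power and two-sided 0.05. With log10(GMR) = (1.960 + 1.282) × SD × √(2/90), the results are 1.56, 1.74 and 1.95 for SD 0.4, 0.5 and 0.6. The noncentral t distribution gives 1.564, 1.750 and 1.957. The stated 1.57, 1.75 and 1.96 are reproduced. The table supposes 90 on Novavax, which under 1:1:1 needs 3 × 90 = 270 randomised before the arm closed.

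**2. Who is in each comparison.**

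| | Before the change | After the change |
|---|---|---|
| Allocation | 1:1:1 | 1:1, no Novavax |
| Priming route | study or community | study only |
| Boost window | day 56–70, or day 56 onward if community-primed | day 56–70 |
| Novavax arm | open | closed |
| Full and one-third BNT162b2 | 1:1 to each other | 1:1 to each other |

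The last row is why one-third versus full dose escapes the problem: both arms draw on each period in the same ratio.

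**3. Share of later controls.** The number randomised before the change, N1, is not given, so it is assumed. With 270 in total, Novavax has N1/3 and the full-dose arm has N1/3 + (270 − N1)/2.

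| N1 (assumed) | Novavax | Full dose | Later share f |
|---|---|---|---|
| 90 | 30 | 120 | 90/120 = 75% |
| 150 | 50 | 110 | 60/110 = 55% |
| 180 | 60 | 105 | 45/105 = 43% |

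**4. Illustrative bias, no true Novavax effect.** Suppose later controls differ from earlier ones by a factor g in post-boost titre. The values 1.25 and 1.5 are assumptions. Then:
- bias b = f × log10(g), and the spurious GMR factor is 10^b (or its inverse, depending on direction);
- SE = SD × √(1/n_Novavax + 1/n_full);
- type I error = P(|Z + b/SE| > 1.96), ignoring the small extra variance from mixing periods.

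Low end: N1 = 180, g = 1.25, SD 0.5. b = 0.4286 × 0.0969 = 0.0415, a factor of 1.10. SE = 0.5 × √(1/60 + 1/105) = 0.0809. b/SE = 0.513, so type I error is 0.081.

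High end: N1 = 90, g = 1.5, SD 0.4. b = 0.75 × 0.1761 = 0.1321, a factor of 1.36. SE = 0.4 × √(1/30 + 1/120) = 0.0816. b/SE = 1.618, so type I error is 0.366.

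With g = 1, b = 0 and the error stays at 5%.

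**5. Sensitivity to the size of the full-dose arm.** If that arm stops at 90, f becomes 60/90 = 67%, 40/90 = 44% and 30/90 = 33%. The factor then runs from 10^(0.333 × 0.0969) = 1.08 to 10^(0.667 × 0.1761) = 1.31. The same formulas give a type I error from 7% (N1 = 180, g = 1.25, SD 0.5) to 29% (N1 = 90, g = 1.5, SD 0.4).

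**The case against.** The strongest reply is that section 12.2 is a summary. It promises a detailed analysis plan signed before any analysis, and choosing which participants enter a comparison is normal content for that plan, which is not shown here. This stands in part. A reader might infer that the sponsor has decided to use the whole homologous arm; the text does not say so. That reading follows only from the absence of a restriction. But the protocol does name the reference arm and the tests. Section 12.4 was updated for the new design, while 12.2 and the 90 per arm in 12.1 were left. An analysis plan that simply follows 12.2 would pool the controls.

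A reader might also infer that the Novavax result is biased and that its interval misses the true effect. The documents do not support that: enrolment by date and any period effect are unknown, so bias is a risk of unknown size and sign.

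Nor does a difference in priming mean a different vaccine. Everyone was primed with BNT162b2, and study-primed participants could also be randomised before the change. The open-ended community interval is limited by the calendar: a 12- to 15-year-old primed under the 13 September 2021 advice and boosted by 29 November had at most 77 days. The study-primed window can itself be exceeded around other vaccinations (section 9.6.1.2), and community enrolment is only temporarily suspended.

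Stratifying by baseline serostatus helps only partly. It applies where a result is available, community-primed participants have no D0 sample, and the planned tests do not use the strata.

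Finally, the primary analysis is called descriptive, immunogenicity is secondary, and the sponsor has moved its focus away from Novavax. This stands, and it lowers the severity.

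**Conclusion.** The point holds as a should-fix. Followed as written, section 12.2 would put into the Novavax comparison, for reactogenicity and GMR alike, controls who could not have been allocated Novavax. That comparison is then not protected by randomisation and could be biased in either direction.

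The factor of 1.10 to 1.36 and the error rate of 8% to 37% are illustrations. They rest on assumed enrolment before closure, recruitment to 270, an assumed 1.25- to 1.5-fold titre difference and a log10 SD of 0.4 to 0.5. They are not estimates for this trial. The one-third versus full-dose comparison, now the focus of the study, is not affected in this way.

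**What to change.** State in section 12.2, and carry into the analysis plan:
- Novavax versus full-dose BNT162b2, for reactogenicity and immunogenicity, uses only participants randomised under the 1:1:1 scheme, identified by randomisation date.
- One-third versus full dose uses all randomised participants, with randomisation period as a stratum or covariate.
- Any Novavax analysis with pooled controls is a labelled sensitivity analysis, adjusted for period, priming route, prime-boost interval and pre-boost serostatus.

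The precision in section 12.1 should be restated for the actual Novavax arm size.

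The change is a few sentences and needs no new data. The cost is a wider Novavax interval. By the formula in step 1 with SD 0.4, the minimum detectable GMR with 60 Novavax participants is 1.72 against 60 concurrent controls and 1.62 against 105 pooled controls. With 30 Novavax participants it is 2.16 against 30 and 1.84 against 120 (√(1/n_Novavax + 1/n_full) replaces √(2/90)).

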Many young people in the UK have already been infected with COVID-19. It is important to understand the response to vaccination in this group. Therefore, participants enrolled in this study will include those with previous proven or suspected COVID-19.

Young people aged 12 to 17 years are now being invited to receive Pfizer-BioNTech vaccine, and many may have already received one dose by the time the study commences. Individuals who have received one dose of Pfizer-BoiNTech vaccine in the community will be eligible to enrol in the study at least 8 weeks after receiving their first dose.

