12. STATISTICS

12.1. Sample size

The total sample size of this trial will be up to 270 Since the primary endpoint analysis will be descriptive and therefore no formal sample size calculation is carried out to determine the sample size of the trial. The number has been therefore chosen based on practical constraints. The precisions on estimating the systematic reactions based on 90 per arm are:

True event rate	Precision (normal approximation)	95% exact binomial CI
5%	±4.5%	1.5%-11.7%
10%	±6.2%	4.7%-18.1%
25%	±8.9%	16.5%-35.2%
50%	±10.3%	39.3%-60.7%

For secondary endpoints of immunogenicity, the minimum geometric mean ratios that can be detected with 90% power at two-sided 0.05 based on 90 per arm are:

Standard deviation on log10 scale	Minimum GMR to detect
0.4	1.57 (or 0.64)
0.5	1.75 (or 0.57)
0.6	1.96 (or 0.51)

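### Section 12.2 compares immunogenicity between arms without adjusting for the pre-boost value or the randomisation strata: valid, but the GMR intervals are likely wider than they need be

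*Protocol*

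**What the plan says.** Protocol section 12.2 fixes the test for continuous immunogenicity outcomes: "Comparisons of continuous immunogenicity data between different arms or at different time points will be made using a t-test" where log-transformation gives approximate normality. "Otherwise, Mann Whitney U test will be used". A separate sentence gives the effect measure: "The GMRs and CIs post boost will be calculated for each of the heterologous arms when comparing to the homologous arm". No covariate, stratum term or regression model appears. The section describes itself as an outline and refers to a full SAP to come.

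Section 9.4 sets the design: "Randomisation will be performed at the time of the second dose", and allocation is "stratified by study site and anti-nucleocapsid IgG status at baseline (where available". It begins with "Participants will be randomised 1:1:1 to the three study groups" and changes to 1:1 between the two BNT162b2 arms after 29 November 2021.

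The population is mixed by intention. Section 5 says that "participants enrolled in this study will include those with previous proven or suspected COVID-19", and section 6 makes the comparison of seropositive with seronegative participants a secondary objective.

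Appendix C lists anti-spike IgG, anti-N IgG and ELISpot at D56, without the mark that limits D0 tests to participants primed in the study. Section 9.6.2 confirms that community-primed participants are also bled at D56.

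**The concern.** Because randomisation happens at the boost, the D56 sample is a true pre-treatment baseline for the boost comparison. If it predicts the post-boost response, a two-sample test leaves that predictable variation in the standard error.

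The strata raise a related issue. Stratified allocation removes most between-arm imbalance in site and anti-N status, but an unadjusted standard error still counts the between-stratum variance as noise. The nominal 95% interval then covers more than 95% of the time.

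Precision is what is at stake. Section 12.4 says the design was amended to concentrate on the immune response to the full and one-third BNT162b2 doses, with results going to JCVI. The section 12.1 table shows that 90 per arm detects only fairly large ratios, and section 12.4 leaves the sample size open to review. A narrower interval would make it easier to detect, or to rule out, a lower response in the one-third-dose arm.

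**Working it through.** **Inputs from the Protocol.** Section 12.1: "the minimum geometric mean ratios that can be detected with 90% power at two-sided 0.05 based on 90 per arm are" 1.57, 1.75 and 1.96 for log10 SDs of 0.4, 0.5 and 0.6. Allocation is equal within each pairwise comparison (section 9.4).

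**Input not in the Protocol.** The correlation r between the log10 post-boost response and the baseline covariates is not given. I assume 0.3 to 0.7.

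**Step 1: reproduce the plan's table.** For an unadjusted two-sample comparison,

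GMR = 10^(SD × √(2/90) × (1.960 + 1.282)).

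Here √(2/90) = 0.1491, and 0.1491 × 3.242 = 0.483. At SD 0.5 the exponent is 0.242 and the GMR is 1.744. The normal approximation gives 1.561, 1.744 and 1.950 for the three SDs. The noncentral t gives 1.564, 1.750 and 1.957. The stated table is reproduced within rounding, so the planning figures also assume no adjustment.

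**Step 2: adjust for baseline.** In an analysis of covariance the residual SD is SD × √(1 − r²). The interval width on the log scale shrinks by the same factor:

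- r = 0.3: √0.91 = 0.954, about 5% narrower
- r = 0.5: √0.75 = 0.866, about 13% narrower
- r = 0.7: √0.51 = 0.714, about 29% narrower

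Detectable GMR at 90 per arm and 90% power (noncentral t):

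| log10 SD | unadjusted | r = 0.3 | r = 0.5 | r = 0.7 |
|---|---|---|---|---|
| 0.4 | 1.564 | 1.532 | 1.473 | 1.377 |
| 0.5 | 1.750 | 1.705 | 1.623 | 1.491 |
| 0.6 | 1.957 | 1.897 | 1.788 | 1.615 |

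At SD 0.5 and r = 0.3 the normal approximation gives 1.700, so about 1.70 is a fair summary.

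The sample size per arm at which an adjusted analysis matches the unadjusted precision of 90 is 90 × (1 − r²): 81.9, 67.5 and 45.9, or about 82, 68 and 46.

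**Step 3: coverage after stratified allocation.** I used 4,000 simulated trials of 90 per arm in which a binary stratum factor, exactly balanced between arms, had correlation r with the response. The unadjusted 95% interval covered 96.3%, 97.8% and 99.3% of the time at r = 0.3, 0.5 and 0.7. The stratum-adjusted interval covered 95.5%, 94.9% and 95.4%. The unadjusted interval is therefore conservative. Exact balance is the extreme case. With several sites and incomplete blocks, the over-coverage would be smaller.

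**The case against.** **The SAP may settle it.** Section 12.2 is an outline and covariates are commonly left to the SAP. That is fair as far as it goes, and the SAP may already contain an adjusted model. But the protocol is not silent here: it names the tests, and they are unadjusted ones. The point concerns a stated method.

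**The construction of the GMR interval is not stated.** This stands. That the intervals follow the t-test is the natural reading, not the protocol's own words.

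**The method is valid.** This stands too. A reader might infer that ignoring the strata biases the comparison or inflates type I error. The documents do not support that: allocation is randomised, and the unadjusted interval errs on the conservative side. The endpoints are also secondary, the primary analysis is descriptive, and sample size was set by practical constraints.

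**The gain rests on assumption.** No correlation, seropositive share or titre difference is given. At r = 0.3 the gain is small. A separate estimate for serostatus would need three assumptions: 50% seropositive, a threefold titre difference and a within-group SD of 0.4. These give 1 − 0.16/(0.16 + 0.25 × 0.477²) = 26% of the variance. That overlaps with what the D56 titre already explains, so it cannot be added to the gain above.

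**Imbalance in prior infection.** A reader might infer that infection history is left unbalanced throughout. Study-primed participants have a D0 anti-N test that can serve for stratification. Community-primed participants have no D0 sample, but section 7.3 suspends their enrolment after 29 November 2021. The worry is confined to community-primed participants randomised before then, whose number is not given.

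**Mann-Whitney U.** It does not estimate a GMR, but the protocol does not present it as doing so. It is meant for data that stay non-normal after log-transformation, where a geometric mean may be a poor summary. A rank-based analysis keeps a place.

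**Conclusion.** The point holds as one of efficiency. Section 12.2 names unadjusted tests although a pre-randomisation value of the same assay is collected from everyone and the design stratifies on factors it treats as relevant. For any non-zero correlation the direction is clear, apart from a negligible cost in degrees of freedom.

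The size is uncertain. For r from 0.3 to 0.7 the log-scale interval would be 5% to 29% narrower, and the detectable GMR at SD 0.5 would fall from 1.75 to between about 1.70 and 1.49. These figures rest on the assumed correlation, on 90 per arm, and on the GMR interval being the one that goes with the t-test.

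The planned comparison remains valid and the section 12.1 table is correct for it. The change is worth making because it costs almost nothing, not because the results would otherwise be wrong.

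**What to change.** In section 12.2, define the between-arm immunogenicity analysis as a linear regression of log10 response on:

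- arm
- log10 D56 value of the same assay
- study site
- anti-N status, using the D56 result where baseline status is unavailable
- randomisation period (up to or after 29 November 2021), because the allocation ratio changed then and NVXCoV2373 was allocated only in the first period

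Report the back-transformed adjusted GMR with its 95% CI as the main result, and keep the unadjusted GMR as supporting. Retain a rank-based analysis only as a sensitivity analysis, for assays that are not approximately normal after log-transformation. The section 12.1 table can stay, with a note that it assumes no adjustment.

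The cost is a few lines in the protocol and matching text in the SAP, settled before between-arm data are examined. Every covariate is already collected, so no visit, sample or assay is added.

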6. OBJECTIVES AND OUTCOME MEASURES

	Objectives	Outcome Measures	Timepoint(s)
Primary	To evaluate the reactogenicity of heterologous boost at least 8 weeks following BNT162B2 prime vaccine administered to adolescents.	Solicited reactions systemic	7 days after boost immunisation
Secondary	To assess safety of heterologous boost COVID-19 vaccines	Serious adverse events Adverse events of special interest	Throughout the study
	To characterise immunogenicity of heterologous & homologous boost schedules	Anti-spike immunoglobulins	D0*, 56, post prime D 14, 28, 132, 236 post boost
		Anti-nucleocapsid immunoglobulins	D0*, 56 post prime D132, 236 post boost
		Cellular immune responses by ELISpot	D0*, 56 post prime

			D 14, 132, 236 post boost
	To assess reactogenicity and safety of heterologous and homologous boost schedules of COVID-19 vaccines	Solicited local reactions	7 days after prime* and boost immunisation
		Unsolicited reactions	28 days after prime* and boost immunisation
	To evaluate immunogenicity, safety & reactogenicity of COVID-19 vaccines in participants seropositive for SARS-CoV-2 nucleocapsid IgG at enrolment, compared with seronegative	Immunogenicity, safety & reactogenicity endpoints as outlined above	Timepoints as outlined above
Exploratory	To assess incidence of SARS-CoV-2 infection in participants receiving heterologous & homologous prime/boost schedules	Self-reported SARS-CoV-2 infection, from community testing	Throughout the study
	To further characterise the blood antibody response	Neutralizing and Functional antibody assays	D0*, 56 post prime D 14, 28, 132, 236 post boost
	To characterise and compare the mucosal immune response to immunisation with homologous and heterologous COVID-19 vaccines using nasal fluid (collected using SAM-strips) and saliva samples	IgA & IgG ELISA and exploratory immunological assays	D0*, 56 post prime D14 post boost
	To determine normal ranges of markers of cardiac muscle damage in adolescents, and to assess change post-immunisation	High sensitivity troponin and N-terminal pro B-type natriuretic peptide (NT-proBNP)	D0*, 56 post prime D14, 28 post boost

* Only for participants receiving prime vaccination in the study

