At the D56 visit blood samples will be taken (as will nasal fluid and saliva samples, if consent has been given for this); booster vaccine will be determined by randomisation and administered; an e-diary will be supplied. These procedures will occur in the same way as described for those participants receiving their first dose of COVID-19 vaccine in the study.

Visits after D56 (i.e. D 14, 28, 132, 236 post boost), will involve the same procedures for all participants, whether or not they received their first dose of COVID-19 vaccine in the study or community. These are described in APPENDIX A: SCHEDULE OF PROCEDURES.

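### Section 12.2 names Mann Whitney U as the fallback for time-point comparisons in the same participants, which ignores pairing, and does not say that the t-test is paired

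*Protocol*

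**What the plan says.** Under Immunogenicity, Section 12.2 of the protocol states: "Comparisons of continuous immunogenicity data between different arms or at different time points will be made using a t-test if normal distribution can be rendered" by taking logs. The next sentence gives the alternative: "Otherwise, Mann Whitney U test will be used". This one rule is the only test named for continuous immunogenicity data. The protocol mentions no paired test, signed-rank test or repeated-measures model.

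The sampling is repeated in the same people. Section 9.6.2 says: "Visits after D56 (i.e. D 14, 28, 132, 236 post boost), will involve the same procedures for all participants". Appendices A and C show blood at D56 before the boost and at those four visits after it. D0 blood is marked as taken only when the first dose was given in the study.

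The one immunogenicity contrast that Section 12.2 spells out is between arms: "The GMRs and CIs post boost will be calculated for each of the heterologous arms when comparing to the homologous arm". Section 12.1 says that "the primary endpoint analysis will be descriptive".

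**The concern.** The rule treats two different problems as one. Between arms at a single visit the samples are independent, and a two-sample t-test or Mann Whitney U is suitable. Between two visits within an arm, each person supplies both values, so the variance of the change contains a covariance term that an independent-samples test leaves out. With positively correlated repeat values, that test overstates the standard error, gives p-values that are too large and loses power.

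The fallback is likely to be used. Section 12.2 itself allows that ELISpot responses may still be non-normal on the log scale and provides medians and interquartile ranges for that case. Section 6 lists ELISpot as a secondary outcome at five time points. What is at stake is any test of the rise after the boost, or of waning up to D236, made under this rule.

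A second problem concerns who is compared. An unpaired comparison of D0 with a later visit, using every available sample, sets study-primed participants alone against a mixture of study-primed and community-primed participants. The estimated change can then be biased in either direction, which goes beyond lost power.

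**Working it through.** **Inputs from the protocol.** Section 12.1 gives 90 per arm, two-sided 0.05, 90% power, and standard deviations (SD) of 0.4, 0.5 and 0.6 on the log10 scale. Its table is introduced by "the minimum geometric mean ratios that can be detected with 90% power at two-sided 0.05 based on 90 per arm are".

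**Assumptions not in the protocol.** Within-person correlation r of log values from 0 to 0.7; equal SD at both visits; 90 complete pairs in one arm.

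**Step 1: reproduce the protocol's table.** For two independent arms, GMR = 10^[(1.960 + 1.282) × SD × √(2/90)]. At SD 0.5 the exponent is 3.242 × 0.5 × 0.1491 = 0.2416, so GMR = 1.74. For SD 0.4 / 0.5 / 0.6 the normal formula gives 1.56 / 1.74 / 1.95, and the t-based version gives 1.56 / 1.75 / 1.96. The protocol states 1.57 / 1.75 / 1.96, so the table is sound for what it covers, which is independent arms.

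**Step 2: standard errors for two visits in one arm.** Unpaired SE = SD × √(2/n). Correct paired SE = SD × √(2(1 − r)/n). Their ratio is 1/√(1 − r).

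**Step 3: normal-theory effect of ignoring the pairing.** True two-sided type I error = 2 × [1 − Φ(1.96/√(1 − r))]. For a change that a paired test detects with 90% power, the unpaired test has power Φ(3.242 − 1.96/√(1 − r)). At r = 0.5 this is Φ(3.242 − 2.772) = Φ(0.470) = 68%. At r = 0.7 it is Φ(3.242 − 3.578) = Φ(−0.336) = 37%.

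**Step 4: Mann Whitney U itself, by simulation.** 20,000 runs of 90 pairs with bivariate normal log values:

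| r (assumed) | Unpaired SE / paired SE | Mann Whitney type I error (nominal 5%) | Mann Whitney power | Paired t-test power |
|---|---|---|---|---|
| 0 | 1.00 | 4.7% | 88% | 89% |
| 0.3 | 1.20 | 2.0% | 79% | 90% |
| 0.5 | 1.41 | 0.6% | 65% | 90% |
| 0.7 | 1.83 | 0.1% | 34% | 89% |

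At r = 0 the standard error is right. The small gap there between 88% and 89% comes from using ranks on normal data, not from pairing.

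**Step 5: which changes are affected.** At SD 0.5 the paired test has 90% power for a 1.59-, 1.48- or 1.36-fold change at r = 0.3, 0.5 or 0.7. An unpaired t-test with 90 values at each visit has at least 90% power for about a 1.75-fold change. The loss therefore falls mainly on moderate changes; a large rise after the boost would be detected either way.

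**Step 6: who contributes to each visit.** By Appendices A and C, D0 has study-primed participants only, while D56 onward has both groups. The D56 window is day 56 to 70 after a study prime but has no upper limit after a community prime. D0 and later visits therefore differ in membership, and later visits also mix prime-to-boost intervals. No figure in the protocol allows this bias to be sized.

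**The case against.** The wording can be read another way. Time points follow the word at, so the sentence may mean arm comparisons made at each visit, for which both tests are valid. The only contrast spelled out and the table in Section 12.1 are both between arms, and no test of a rise or of waning is named. This ambiguity is real. However, the sentence joins arms and time points with or, which more naturally makes time a second kind of comparison. If arm comparisons at each visit are meant, the text should say so.

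A second objection is that Section 12.2 is a summary and a full analysis plan is to follow. That answers the t-test branch, where paired or unpaired is ordinary detail. It does not answer the fallback, because the protocol names a specific independent-samples test.

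Third, pairing has a cost: participants with only one of the two samples drop out, and Section 12.3 already makes general provision for missing data. The cost is real but small beside comparing visits with different membership.

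A reader might infer three stronger things that the protocol does not support:

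- That every within-person change is assigned an independent-samples test. Only the fallback certainly is; the t-test could be run paired.
- That false positives result. With positive correlation the type I error falls below 5%.
- That the cardiac-marker objective, "To determine normal ranges of markers of cardiac muscle damage in adolescents, and to assess change post-immunisation", inherits the error. The rule is limited to immunogenicity data, and those markers are a separate exploratory objective.

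**Conclusion.** The point holds on the plain reading of Section 12.2. For time-point comparisons in the same participants, the named fallback is the wrong test and the t-test is left unlabelled. Over an assumed r of 0.3 to 0.7, the standard error is 1.20 to 1.83 times too large, and Mann Whitney power is about 79% down to 34% where a paired t-test has about 90%. At r = 0 ignoring the pairing costs nothing.

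These figures also rest on equal SDs, 90 complete pairs and normal log values. The fallback would be used when log values are not normal, so the power figures are a guide to direction and size rather than exact values. The D0 membership problem does not depend on r.

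Reach is limited to secondary, within-participant immunogenicity comparisons. The descriptive primary analysis, the between-arm geometric mean ratios and the table in Section 12.1 stand as they are. The sentence should be corrected, but the trial's main conclusions do not depend on it.

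**What to change.** Split the sentence in Section 12.2 into two rules and carry both into the analysis plan.

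- Between arms at one time point: keep the two-sample t-test on log values, or Mann Whitney U if they are not normal.
- Between time points within participants: use a paired t-test on log10 differences, reported as a geometric mean fold change with 95% CI, or the Wilcoxon signed-rank test if the log differences are not normal. Include participants with both samples, and report how many there are. Comparisons with D0 are then confined to study-primed participants.

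The cost is one sentence in the protocol and its counterpart in the analysis plan, with no new data. The small downside is that a participant with only one of the two samples does not contribute to that comparison.
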